7.2.3 TEAE Resulting in Death

If there are any TEAE that result in death for either part of the study, then a listing of all deaths will be provided for that part of the study.

7.2.4 TEAE Leading to Study Discontinuation

For Part A subjects receive only a single dose of study medication which precludes drug withdrawal in response to an adverse event. 'Drug Withdrawn'. The subjects who experience adverse events leading to study discontinuation during Part A will be captured in the disposition listing.

For Part B, adverse events for resulting in drug discontinuation (designated as 'Drug Withdrawn') will be classified as a TEAE leading to study drug discontinuation. TEAEs that lead to study drug discontinuation will be summarized for each treatment group by SOC and PT for the Safety population. A by-subject listing of the TEAE that lead to study drug discontinuation will also be provided.

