6.1.1. Part A: Single Ascending Dose with Food Effect Design

Part A will comprise a double-blinded, 2-staggered, alternating, 3- or 4-period sequence design of single ascending doses in statin-free, overweight (body mass index [BMI] 25.0 to 35.0 kg/m²),

healthy male and female subjects, investigating the safety, tolerability, and PK of single doses of LY3202328 administered in the fasted state. One dose level will be repeated in the fed state using the same randomization as conducted in the fasted state to assess the effect of food on LY3202328 exposure.

A total of 18 subjects will be enrolled in 2 cohorts. Cohort 1 will consist of 3 periods at dose levels 1, 10, and 100 mg, and Cohort 2 will consist of 3 periods at dose levels 3, 30, and 300 mg. A fourth dosing period will be added to either Cohort 1 or Cohort 2 to assess exposure differences when LY3202328 is administered in a fed state. Each cohort will consist of 9 subjects where subjects will receive either a single LY3202328 dose or a corresponding placebo in alternating ascending order.

In each cohort, 6 subjects will receive LY3202328 and 3 subjects will receive placebo. Subjects will be dosed in the fasted state in all periods except for subjects in the cohort that will return for the fourth dosing period to repeat 1 dose level (planned 30 mg dose level) in the fed state to evaluate food effects on LY3202328 exposure. An additional potential cohort (not evaluated for food effect) will be reserved for the fourth dosing period at a higher dose level (600 mg). Escalation to this higher dose will only be made if exposure continues to increase between 100 and 300 mg dose levels and the safety profile supports dosing to a higher level.

Potential subjects will be screened to assess their eligibility to enter the study within 42 days prior to study entry (i.e., prior to Check in for Part A). Subjects will be confined at the clinical research unit (CRU) from Day –1 (the day before dosing) to Day 2 (24 hours postdose), and return on Days 3 and 5 (48 and 96 hours postdose, respectively) for follow-up assessments. Dosing in subsequent periods will be approximately 2 weeks after dosing in the prior period, with subjects dosed on Day 1 of Week 1, 3, or 5 (Cohort 1); Week 2, 4, or 6 (Cohort 2); and Week 8 (food effect period, Cohort 2).

Treatment of the cohorts in Part A will be staggered so that the appropriateness of escalation to the next dose level can be determined from the current dose level.

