6.2. Number of Participants

Eighteen healthy males and female subjects may be enrolled in Part A where each subject is scheduled to receive 2 single doses of LY3202328 and 1 dose of placebo in ascending dose levels. Forty subjects may be enrolled in Part B (8 subjects will receive LY3202328 and 2 subjects will receive placebo in each of 4 dose level cohorts). Additional subjects may be enrolled to replace drop-outs or discontinued subjects, but are not required. Replacement subjects may complete any portion of the study as needed, i.e. any portion not completed by the discontinued subject with the goal to complete up to 18 subjects in Part A and up to 40 subjects in Part B. The decision to replace subjects will be discussed with the Sponsor prior to adding subjects.

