8.2. Method of Treatment Assignment

Subjects who meet all criteria for enrollment during Part A will be assigned to a randomization sequence number by the CRU on Day –1 within Cohort 1 (1, 10, and 100 mg) or Cohort 2 (3, 30, and 300 mg) that corresponds to 1 of the 3 treatment sequences in a 1:1:1 ratio so that 6 subjects receive LY3202328 and 3 subjects receive placebo, per dose level if all subjects are retained on study. The 30 mg dose level in Cohort 2 will be repeated in Period 4 to evaluate food effects on exposure.

Subjects who meet all criteria for enrollment during Part B will be stratified evenly to the simvastatin DDI assessment and the atorvastatin DDI assessment and assigned a randomization number on Day –7 of Part B for each cohort (Cohorts 3, 4, 5, and 6 at 5, 20, 100, and 300 mg, respectively, planned) in the order in which they were enrolled into the study. For each cohort, subjects will be randomly assigned 4:1 to receive LY3202328 or placebo within each stratum.

Randomization for Parts A and B will be performed in accordance with the randomization schedule generated by Chorus (or designee).

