1.3 Study Design with Sample Size Justification

Study I8Q-MC-GSEA(a) (GSEA) is a first-in-man, Phase 1, randomized, double-blind, placebo-controlled, 2-part, ascending single- and multiple-oral dose study of LY in overweight, healthy subjects (Part A) and in dyslipidemic, statin-free, overweight, healthy subjects with a statin drug-drug interaction (DDI) assessments (Part B).

This study will be conducted in 2 parts: Part A, a single ascending dose (SAD) study design at a single site and Part B, a multiple ascending dose (MAD) study design conducted in multiple sites.

Eighteen statin-free, overweight, healthy males and female subjects may be enrolled in one of two 9-subject cohorts in Part A. Each subject is scheduled to receive 2 single doses of LY and 1 dose of placebo in ascending dose levels. This sample size is customary for Phase 1 studies evaluating safety, tolerability, and pharmacokinetic parameters, and is not powered on the basis of statistical hypothesis testing.

Forty statin-free, overweight, dyslipidemic subjects may be enrolled in Part B. Subjects will be enrolled in one of four dose-ascending 10-subject cohorts (8 subjects will receive LY and 2 subjects will receive placebo in each cohort). This sample size is a customary sample size for a Phase 1b MAD study evaluating safety, tolerability, and pharmacokinetic parameters.

2 General Statistical Methodology and Conventions

Chorus will designate a provider to generate the statistical analyses detailed in this SAP. All computations for statistical analyses will be performed using SAS® software, Version 9.3 or later. All SAS programs used in the production of statistical summary outputs will be validated with independent programming prior to finalization. In addition, all program outputs will be independently reviewed. The validation process will be used to confirm that all data manipulations and calculations were accurately done. Once validation is complete, a senior statistical reviewer will perform a final review of the documents to ensure the accuracy and consistency with this plan and consistency within tables. Upon completion of validation and quality review procedures, all documentation will be collected and filed by the project statistician or designee.

For the implementation of parametric methods of analysis, residual plots will be examined to determine if model assumptions are satisfied. Transformations or nonparametric methods of

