2.2.2 Treatment Groups

During Part A, subjects will be treated in multiple dosing periods with single doses of a subset of the treatments -- Placebo, and 1mg, 3mg, 10mg, 30mg, 100mg, 300mg, or 600mg of LY. Dosing will be performed in a fasted state, except in the fourth dosing period for Cohort 2 when subjects will be dosed with 30mg LY after a standard meal. The treatment groups for Part A will be the dose levels of LY, plus the group 30mg LY fed.

During Part B, subjects will be enrolled in one of four dose-ascending groups (5mg LY, 20mg LY, 100mg LY, and 300mg LY) where they will be randomized to receive LY or placebo. The treatment groups for Part B will be Placebo, 5mg LY, 20mg LY, 100mg LY, and 300mg LY.

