2.3 Handling of Dropouts and Missing Data

Summaries are primarily based on the Safety population, and safety data will be reported for all available subjects. In situations where Subjects in Part A discontinue early from the study, replacement subjects may be included for subsequent dosing periods.

Analyses of the PD endpoints will be performed using mixed-effects model repeated measures (MMRM). This methodology mitigates the impact of missing data, which will be assumed to be missing at random during the study.

Imputation of missing or partial dates is not expected, but if a complete date is required for calculations, the following algorithms will be applied:

- For the start date:
 - If year, month, and day are missing then use the minimum of the subject's first visit date or the consent date.
 - If either only month or month and day are missing then use January 1.
 - If only day is missing, impute the first day of the month.
- For the end date:
 - If year, month, and day are missing then use the subject's last visit date.
 - If either only month or month and day are missing then use December 31.
 - If only day is missing then use the last day of the month.
 - Do not expand the record past the subject's last visit.

The original missing or partial date, the imputed complete date, and the indicator variable identifying dates that were imputed will be retained in the database.

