7.2.5 Treatment-Related TEAE

Every AE will be assessed by the investigator for its relationship to study medication. The TEAEs either assessed by the investigator to be possibly, probably, or definitely related to study treatment or that are missing the investigator's assessment will be categorized as treatment-related TEAEs.

The tabled results for all TEAE, serious TEAE, and TEAE that lead to study discontinuation will be repeated for Parts A and B using the subset of TEAE that are classified as treatment-related.

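### SAP 7.2.4 treats Part A as one dose per subject, so Part A has no definition and no SOC/PT table of TEAEs leading to discontinuation, although SAP 7.2 and 7.2.5 call for that result

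*SAP*

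**What the plan says.** SAP 7.2.4 gives the reason for handling Part A differently: "For Part A subjects receive only a single dose of study medication which precludes drug withdrawal in response to an adverse event". It then sends Part A subjects whose adverse events lead to study discontinuation to the disposition listing. Part B gets a definition based on the drug-withdrawn designation, a table by system organ class (SOC) and preferred term (PT), and a by-subject listing of the events.

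The design sections describe Part A as follows:
- SAP 1.3: "Each subject is scheduled to receive 2 single doses of LY and 1 dose of placebo in ascending dose levels". Protocol 6.2 agrees: "each subject is scheduled to receive 2 single doses of LY3202328 and 1 dose of placebo in ascending dose levels".
- SAP 2.2.2: "During Part A, subjects will be treated in multiple dosing periods with single doses of a subset of the treatments".
- Protocol 6.1.1: "Dosing in subsequent periods will be approximately 2 weeks after dosing in the prior period".
- SAP 2.3 provides for dropout between periods: "In situations where Subjects in Part A discontinue early from the study, replacement subjects may be included for subsequent dosing periods".

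Two other parts of the safety section assume that a Part A category exists. SAP 7.2 plans a TEAE overview for both parts by treatment group, built on the TEAE types in its subsections. SAP 7.2.5 states: "The tabled results for all TEAE, serious TEAE, and TEAE that lead to study discontinuation will be repeated for Parts A and B", restricted to treatment-related events.

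**The concern.** A subject with two or three doses still to come can have them withheld because of an adverse event. The reason 7.2.4 gives for having no Part A table therefore fails.

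Safety and tolerability of single doses is part of the primary objective (Protocol 5.1, SAP 1.2.1), and Part A sets the maximum tolerated dose that caps Part B (Protocol 8.3.1). A reader of the Part A tables would want to know which events, at which dose, led subjects to stop, and whether the investigator judged them related. There is also a programming problem: 7.2 and 7.2.5 ask for Part A results in a category that 7.2.4 does not define.

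**Working it through.** No test or sample-size formula is involved. SAP 7.2 rules out statistical testing of TEAEs. The check is a count of doses, then a comparison of sections.

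**Step 1. Doses per subject.** The inputs are the sequences in Protocol Figure GSEA.1 and the allocation in Protocol 8.2: "1 of the 3 treatment sequences in a 1:1:1 ratio so that 6 subjects receive LY3202328 and 3 subjects receive placebo, per dose level". In each of the six sequences, Periods 1 to 3 contain 2 LY3202328 doses and 1 placebo dose, so 2 + 1 = 3. This reproduces the figure in SAP 1.3 and Protocol 6.2. Cohort 2 has a fourth dose in the food-effect period.

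**Step 2. Administrations followed by another scheduled dose in the same subject.**

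| Cohort, period | LY dose | On LY | On placebo | Later dose scheduled? |
|---|---|---|---|---|
| 1, Period 1 | 1 mg | 6 | 3 | yes |
| 1, Period 2 | 10 mg | 6 | 3 | yes |
| 1, Period 3 | 100 mg | 6 | 3 | no |
| 2, Period 1 | 3 mg | 6 | 3 | yes |
| 2, Period 2 | 30 mg | 6 | 3 | yes |
| 2, Period 3 | 300 mg | 6 | 3 | yes |
| 2, Period 4 | 30 mg fed | 6 | 3 | no |

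- All administrations: 7 × 9 = 63.
- Followed by another dose: 5 × 9 = 45, of which 5 × 6 = 30 are LY3202328 and 5 × 3 = 15 placebo. 45/63 = 71%.
- Periods 1 to 3 only: 18 × 3 = 54 administrations, of which 36 (67%) are followed by another dose.
- If Cohort 1 also returns for 600 mg, as SAP 2.1 describes: 63 + 9 = 72 administrations, of which 54 (75%) are followed by another dose.

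If 7.2.4 were right, the share followed by another dose would be zero.

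**Step 3. Do the documents expect Part A stopping?** Yes. Protocol 9.1 prescribes end-of-study procedures for subjects who stop the product early and names the single-dose part explicitly (Day 5). SAP 2.3 plans for replacements.

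**Step 4. What each planned Part A output would show.**

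| Output | Shows the event (SOC/PT) | Shows that it led to stopping | By treatment |
|---|---|---|---|
| Disposition table (SAP 3.2) | no | as an eCRF reason, if the list has an adverse-event reason | yes |
| All TEAEs (7.2.1) | yes | no | yes |
| Related subset of all TEAEs (7.2.5) | yes | no | yes |
| Maximal severity (7.2.6) | yes | no | yes |
| Overview line for this type (7.2) | no | undefined for Part A | yes |
| Discontinuation table, related subset (7.2.5) | no parent table | no parent table | – |

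No planned table links a Part A event to the decision to stop. The overview line and the related-event repeat cannot be produced without a definition that 7.2.4 does not give.

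**The case against.** The best defence is that little information is lost. SAP 3.2 tabulates Part A discontinuations under the most recently received treatment, with the eCRF reason, and uses the number who received that treatment as denominator. The events themselves appear in the Part A SOC/PT, treatment-related and severity tables and, if serious, in the SAE table and listing. SAP 7.2.4 does not deny that an adverse event can end participation: it expects such subjects and directs them to a listing. With six LY3202328 subjects per dose level, a listing may carry most of what a table would. Escalation rests on the data review described in Protocol 8.3.1, not on this table. SAP 1.1 also allows supportive analyses to be added without an amendment.

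Most of this stands. A reader might infer from 7.2.4 that Part A events that stop dosing are never tabulated or drop out of the safety summaries. The documents do not support that, for the reasons just given. A reader might also take 71% as the share of events that would be missed. It is only the share of administrations with a later dose at stake, one third of them are placebo (15/45), and no discontinuation rate is stated anywhere.

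The defence does not restore the premise, and it does not reconcile 7.2.4 with 7.2 and 7.2.5. Nor does it supply the missing link between event and stopping. The only Part A output that 7.2.4 names is a disposition listing, whereas Part B gets an event-level listing.

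**Conclusion.** The point holds in a limited form. The single-dose premise is contradicted by SAP 1.3 and 2.2.2 and by Protocol 6.1.1 and 6.2. As a result Part A has no definition and no SOC/PT table of TEAEs leading to discontinuation, while two other SAP sections presume a Part A result. What is missing is the identity of those events and their related subset. The count of discontinuations by treatment is planned.

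The consequence is modest: there are 18 subjects, no test is involved, and the listings give partial cover. It is still worth correcting before the outputs are programmed.

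Assumptions:
- The eCRF reason list and the table and listing shells are not in the documents. If the list has no adverse-event reason, the SAP 3.2 table would show less than is credited here. If the disposition listing carries event terms and relatedness, the gap is smaller.
- The count of 45 of 63 takes Period 4 in Cohort 2 as planned, with no dropouts or replacements. The 54 of 72 applies only if the 600 mg dose is given to Cohort 1.

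**What to change.** In SAP 7.2.4:
1. Delete the single-dose premise.
2. Define a Part A TEAE leading to discontinuation as one because of which the subject receives no further scheduled dose or leaves the study, including after the last scheduled dose. Without that last clause the 100 mg and 30 mg fed groups, which as planned are final doses, could never contribute an event.
3. Tabulate these events by SOC and PT under the most recently received treatment, the attribution rule already in SAP 7.2, and add a by-subject listing like the one for Part B.
4. Use the same definition for the treatment-related subset in 7.2.5 and the Part A line of the 7.2 overview.

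If the sponsor prefers not to add the table, the minimum is to correct the premise, limit the 7.2.5 statement to Part B for this category, and say how the Part A overview line is obtained.

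The cost is a few lines of SAP text, one listing, and one small table with its related subset, which may be empty. No new data are needed if the adverse-event action-taken and disposition fields are on the eCRF. That is assumed here and should be confirmed.

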7.2.5 Treatment-Related TEAE

Every AE will be assessed by the investigator for its relationship to study medication. The TEAEs either assessed by the investigator to be possibly, probably, or definitely related to study treatment or that are missing the investigator's assessment will be categorized as treatment-related TEAEs.

The tabled results for all TEAE, serious TEAE, and TEAE that lead to study discontinuation will be repeated for Parts A and B using the subset of TEAE that are classified as treatment-related.

7.2.6 TEAE by Maximal Severity

Every AE will be graded by the investigator as mild, moderate, or severe, so for each subject the greatest severity observed can be obtained by comparing the severity of all of a subject's TEAE that share the same SOC or PT. A table of TEAE by maximal severity will be prepared for each treatment arm by SOC and PT for the Safety population. This report will be generated for both Parts A and B.

7.2.7 Treatment-Emergent (not including Serious) Adverse Events

To meet the requirements for reporting on clinicaltrials.gov, the most common non-serious TEAE will be reported for both Parts A and B. All PT that occur in at least 5% of the Safety Population subjects in any treatment group, when not counting the serious TEAE, will be tabulated by SOC and PT for each treatment group. These reports will also present the total number of TEAE for each SOC and PT

7.3 Clinical Laboratory Analyses

Blood samples for hematology and clinical chemistry and urine samples for urinalysis will be collected in both Parts A and B. Profiles for the hematology, clinical chemistry and the numeric urinalysis parameters will be summarized for both Parts A and B.

7.3.1 Clinical Laboratory Analyses in Part A

For Part A, blood samples will be collected pre-dose on Day 1 and at 24, 48 and 96 hours post-dose for all subjects in each dosing period in Part A. The measurements from dosing period 4 for Cohort 2 will not be included in this analysis since dosing of study medication occurred in a fed state.

7.3.1.1 Clinical Laboratory over time in Part A

Change from baseline for each of the hematology, clinical chemistry and the numeric urinalysis parameters will be derived for each of the post-dose time points using the pre-dose measurement as the baseline. Descriptive statistics for the measurement at baseline and the measurement and change from baseline at each post-dose time point will be tabulated.

Plots of the least squares mean \pm standard error estimates for each parameter over time (pre-dose through 96 hours post-dose) will be provided by treatment group.

7.3.1.2 Clinical Laboratory Shift Tables in Part A

Each laboratory parameter will be classified as low, normal or high relative to the central laboratory's normal range. For each treatment group shift tables will be generated from the pre-dose category to the category 96 hours post-dose for each laboratory parameter. The shift tables will present the number (percent) of subjects who started in a category (low, normal, high) at baseline and ended in a category at the end of the study. A missing category will be included for both pre-dose and 96-hours post-dose, so that all subjects in the Safety population will be represented in the table. The percentages will be calculated using number of subjects in the Safety population who have measurements at pre-dose and 96-hours post-dose.

Shift tables comparing pre-dose to the other time points in the study may be generated if warranted after data review.

Similar shift tables for the categorical urinalysis parameter will also be produced using all categories reported for a parameter during the study.

7.3.2 Clinical Laboratory Analyses in Part B

For Part B, blood samples will be collected on Day -1 then pre-dose on Days 2, 7, 14, 21, and 29 and during follow-up on Days 35 and 42 or 56 for all subjects in Part B.

7.3.2.1 Clinical Laboratory over time in Part B

Change from baseline for each of the hematology, clinical chemistry and the numeric urinalysis parameters will be derived for each of the post-baseline time points using the Day -1 measurement as the baseline. Descriptive statistics for the measurement at baseline and the measurement and change from baseline at each post-baseline time point will be tabulated.

Plots of the least squares mean \pm standard error estimates for each lipid parameter over time (baseline through Day 56) will be provided by treatment group.

7.3.2.2 Clinical Laboratory Shift Tables in Part B

For each treatment group shift tables will be generated from the baseline category to the category at Day 42 or 56 for each laboratory parameter. The shift tables will present the number (percent) of subjects who started in a category (low, normal, high) at baseline and ended in a category at the end of the study. A missing category will be included for both baseline and Day 42 or 56, so that all subjects in the Safety population will be represented in the table. The percentages will be calculated using number of subjects in the Safety population who have measurements at baseline and at Day 42 or 56.

Additional shift tables may be generated if warranted after data review.

Shift tables for the categorical urinalysis parameter will also be produced.

